If volunteers complete the informed consent/assent process and are eligible for participation, they will be randomized to double blind varenicline or placebo and will proceed with treatment. In order to avoid accidental bias, we will utilize a stratified urn randomization procedure. We will stratify by the prognostic covariates age (14-17 versus 18-21) and baseline smoking level (<12 versus 12 or more cigarettes per day, based on median baseline smoking in our prior randomized adolescent smoking cessation trial). The age stratification will ensure that both younger and older adolescents will be equally represented in the varenicline and placebo groups. The smoking level stratification will help avoid significantly discrepant baseline smoking between treatment groups. We considered additional stratification variables (e.g., gender, severity of nicotine dependence, presence of other smokers in household, history of attention-deficit/hyperactivity disorder), but, amid concern over excessive division of participants among multiple cells, judged that these could be adequately explored as covariates during efficacy analyses (see Section C3f).

C3d. Treatment

Pharmacological Intervention

The MUSC Investigational Drug Service (IDS) will obtain varenicline 0.5 mg and 1 mg tablets and matched placebo tablets. All tablets will be packaged in blister packs, with individual labels for time/date of each dose (e.g., Tuesday morning October 5th). This date- and time-labeled blister pack method has demonstrated superior participant adherence, compared to traditional packaging, and offers the additional advantage of tracking the exact timing of any missed doses (53-55). The IDS successfully used identical methods for medication/placebo dispensing in our adolescent varenicline pilot study.

If assessment procedures reveal that a participant meets inclusion criteria, the IDS will randomize the participant to varenicline or placebo in double-blind fashion. He/she will be given a 7-day supply of medication to take home. Participants will be given an additional 7-day supply "replacement pack" of medication for use in the event that they cannot make it back for a visit within the 7-day window between visits.

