14. **Multidimensional Scale of Perceived Social Support (MSPSS)** (67, 68): The MSPSS is an adolescent-validated 12-item instrument that assesses perceived support from family, friends, and a significant other.
15. **Barratt Impulsiveness Scale (BIS-11)** (69): The BIS-11 is an adolescent-validated 30-item self-report questionnaire of impulsive personality traits.
16. **Toronto Alexithymia Scale (TAS-20)** (87): The TAS is a scale which measures alexithymia, a condition in which people have trouble identifying and describing feelings. Items are rated using a 5-point Likert scale whereby 1 = strongly disagree and 5 = strongly agree. Both the original, 1985 version and the revised, 1992 version will be administered at the assessment visit.
17. **Wisconsin Predicting Patient's Relapse (WI-PREPARE)** (88): The WI-PREPARE is a 7-item scale that predicts relapse to smoking through assessment of nicotine physical dependence, environmental factors, and individual difference characteristics.
18. **Technology Acceptability Questionnaire**: This 54-item, locally developed questionnaire will be administered to participants once during the course of the study to gain information on their technology use and acceptability.

Psychiatric Symptom Assessments (to be administered at all visits)

1. **Psychiatric Interview**: The study medical clinician (directly supervised by the PI, a board certified child & adolescent psychiatrist) will conduct an interview inquiring about symptoms of depression, mania/hypomania, pathological anxiety, psychosis, substance abuse, sleep disturbance, and suicidality since the last visit. The screening items from the MINI (56,57) will be modified for use as a prompt to evaluate all major components of psychiatric symptomatology.
2. **ADHD Rating Scale-IV (ADHD-RS)** (70): This validated measure will assess ADHD symptom severity.
3. **Hospital Anxiety and Depression Scale (HADS)** (71-73): This self-report instrument, validated in adolescents and adults, will be used to monitor anxiety and depression symptoms.

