Categorical clinical and demographic variables will be assessed by chi-square tests of independence, while continuous variables will be assessed using Student's *t*-test. The effect of varenicline versus placebo on abstinence at end of treatment will be examined using logistic regression. Models will be computed both unadjusted and adjusted for significant covariates found in the descriptive analysis. For these efficacy analyses, 7-day point prevalence abstinence will be defined as having no cigarettes (or other tobacco/nicotine products) for 7 days, confirmed by urine cotinine level ≤ 50 ng/mL. All randomized participants will be included in the analyses (intent-to-treat approach), and participants will be considered non-abstinent at any missed visit.

Safety: Primary Analysis

Similar to adult varenicline phase III studies (23,24), we define any treatment-emergent adverse event any adverse event occurring between treatment initiation and one week following treatment conclusion. Non-inferiority analysis will be utilized to compare adverse event rates between varenicline and placebo groups (84). With a type 1 error rate of 5% ($\alpha = 0.05$) and power ($1 - \beta$) of 80%, the proposed total sample size of 166 and an estimated placebo rate of treatment-emergent adverse events of 75% (23) will afford a non-inferiority margin (NIM) of 16.7% for the varenicline adverse event rate. We considered incorporating a larger sample

Pro00014398

size that would afford a smaller NIM. However, even to detect a 12.5% NIM, a total sample size of 376 participants would be necessary. That sample size would not be feasible within the proposed funding period.

Smoking-Related Outcomes: Secondary Analysis

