Secondary outcomes include the following: a) 7-day biologically confirmed point prevalence abstinence at 6 months, b) continuous abstinence, c) time to lapse (first puff), d) time to relapse (first of 3 consecutive days smoking ≥ 1 cigarette), and e) longitudinal efficacy of varenicline. These will be tested via logistic regression to examine a) point prevalence at 6 months and b) continuous abstinence from targeted quit date (Week 1) to both treatment conclusion (Week 12) and final follow-up visit (Week 26), Cox Proportional hazard models (83) to examine c) time to first lapse (first puff, first cigarette), d) time to relapse (first of 3 consecutive days smoking ≥ 1 cigarette), and e) Generalized Estimating Equation (repeated measures) to examine the entire study time course. Repeated measures analysis of variance will be used to assess treatment effects of varenicline on craving (QSU-B), withdrawal (MNWS), and smoking reinforcement (mCEQ) throughout the study. All efficacy analyses (primary and secondary) will be repeated among participants with $\geq 80\%$ medication adherence, per protocol analysis, and completers analysis. Medication adherence (pill counts), nicotine dependence (mFTQ, AUTOS), motivation/readiness to quit (baseline rating), self-efficacy (GSES), perceived social support (MSPSS), and impulsivity (BIS-11) will be explored as possible moderators influencing the effect of varenicline on abstinence.

Safety: Secondary Analysis

Of particular interest will be adverse events leading to medication discontinuation and the occurrence of treatment-related serious adverse events (SAEs) (see Human Subjects Section 4.6). We will specifically compare neuropsychiatric adverse events (Psychiatric Interview) using non-inferiority testing, as well as depression/anxiety (HADS) and suicidality (C-SSRS) ratings using one-sided 2-sample t-tests. Based on adult literature (34,35), we anticipate no serious adverse events, and appropriate stopping plans are in place (see section C3g) for added precaution.

Participant Retention Analysis

Total number of treatment visits attended will be compared using a Student's *t*-test, while the number of days retained will be assessed using Cox Proportional Hazards regression models.

C3g. Clinical Management Issues

Study Termination

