Study termination may be initiated by a study participant (or parent/guardian, as applicable) for personal reasons, or by the PI or members of the Data Safety and Monitoring Board for reasons of participant safety or the additional requirement for more intensive or a different form of therapy for addiction, medical, or psychiatric disorders. Another cause for termination would be any participant behavior that is felt to present a threat or harm to staff, including sexual or verbal harassment. Other terminations may be due to a participant becoming lost to follow up and/or moving from the geographic area. Frequency counts for reasons for termination will be analyzed for both treatment groups using chi square analytic procedures. If a participant is terminated for any reason, attempts will be made to continue collecting adverse event and smoking data over the 12-week treatment trial and follow-up period so that data can be entered for the intent-to-treat analysis.

Clinical Deterioration "Rescue Plan"

A clinical deterioration "rescue" plan will be in place for participants that experience psychiatric or substance use deterioration during the study. Symptoms will be monitored closely throughout the trial to assess for deterioration. Any participant demonstrating gross clinical deterioration will be discontinued from the trial and appropriate intervention will be arranged. The rescue measures will include withdrawal from the study, immediate assessment by the PI or physician Co-I for a comprehensive psychiatric and substance abuse evaluation and determination of appropriate intervention, as well as emergency therapy sessions if the participant does not meet criteria for withdrawal from the study. In the case that the participant is aged 14-17, the PI will contact the parent/guardian to discuss the clinical deterioration and enlist involvement with proposed intervention. The intervention may include outpatient, day treatment, partial hospitalization, or inpatient treatment in the Medical University of South Carolina Institute of Psychiatry. These programs have highly trained clinicians competent in treating all psychiatric and substance use disorders. The PI holds admitting privileges for all of these clinical programs, allowing for efficient referral and management.

Referral for Participants Needing Continuing Treatment

At the end of the study, if a participant (or parent/guardian, as applicable) requires or requests continuing

Pro00014398

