4.4 Quality Assurance

Accuracy and completeness of the data collected will be ensured by weekly review. A 10% random sample of the primary source document will be crosschecked with the database on a quarterly basis. If inaccuracies exceed 4%, then a second 10% will be randomly chosen for audit. The REDCap system does not accept outliers, illogical response patterns, etc. The PI will have weekly meetings with the research assistants to discuss qualitative comments received during data collection and any problems in data collection or entry. The statistician will periodically examine the database to look for irregularities. Initial data analyses will examine distributions of variable scores and comparability of baseline characteristics across conditions in case analyses need to be adjusted for these. Confidentiality protections are outlined above.

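### HADS is compared by an unadjusted t-test at no named visit, and the craving, withdrawal and reinforcement scales have no baseline term or missing-score rule; a baseline-adjusted mixed model would use the collected data better

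*Combined protocol and SAP*

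**What the plan says.** - **Craving, withdrawal, reinforcement.** C3f, Smoking-Related Outcomes: Secondary Analysis, gives a repeated-measures method for these scales: "analysis of variance will be used to assess treatment effects of varenicline on craving (QSU-B), withdrawal (MNWS), and smoking reinforcement (mCEQ) throughout the study". It names no time points, baseline score, covariance structure, software implementation or rule for missing scores.
- **HADS.** C3f, Safety: Secondary Analysis, compares "depression/anxiety (HADS) and suicidality (C-SSRS) ratings using one-sided 2-sample t-tests". It names no visit, change score or summary. C3e lists HADS under the heading "Psychiatric Symptom Assessments (to be administered at all visits", so a baseline and repeated values exist.
- **Missed visits.** The only rule, in C3f, Efficacy: Primary Analysis, is that "participants will be considered non-abstinent at any missed visit". It fixes a binary outcome and cannot supply a scale score.
- **Baseline adjustment.** Human Subjects section 4.4 says that initial analyses will look at "comparability of baseline characteristics across conditions in case analyses need to be adjusted for these". This is conditional and names neither an outcome nor a model term. The covariate sentence in the primary efficacy text concerns the abstinence models.
- **Strata.** C3c: "We will stratify by the prognostic covariates age (14-17 versus 18-21) and baseline smoking level".
- **Leaving the trial.** C3g: "Any participant demonstrating gross clinical deterioration will be discontinued from the trial". After termination, "attempts will be made to continue collecting adverse event and smoking data over the 12-week treatment trial and follow-up period"; scale scores are not mentioned.

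**The concern.** A two-sample t-test on a score measured at every visit ignores both the participant's own baseline and all the other visits. It is therefore less precise than the data allow. Because no visit is named, the comparison could be chosen after the data are seen.

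Repeated measures ANOVA in its classical form drops anyone with a missing visit, and the plan does not say that another form will be used. Adjusting only when imbalance appears misses the main reason to adjust, which is that a baseline score predicting the later score reduces the variance whether or not the arms happen to differ.

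HADS is one of the psychiatric safety measures, in a trial where psychiatric safety is a stated preoccupation. If participants who deteriorate leave without later scores, a late comparison among attenders could understate worsening.

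**Working it through.** The plan gives no power, SD, correlation or effect size for any of these scales, so there is no plan figure to reproduce. The documents supply 83 per arm (C3f, Sample Size and Power), the one-sided test, and completion of 30-60% in earlier adolescent trials. They also give 84% in the team's 8-week cannabis trial, counting only participants engaged in contingency management (C3b, Retention Strategies). The correlations and the 0.3 SD difference below are assumptions.

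**1. HADS at one visit: value of the baseline score.** Adjusting for a baseline with correlation r multiplies the variance of the treatment difference by 1 - r². In SD units the noncentrality is 0.3 × √(83/2) / √(1 - r²), and √(83/2) = 6.442. One-sided 5% power from the noncentral t:

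| r | 1 - r² | noncentrality | power |
|---|---|---|---|
| unadjusted | 1.00 | 1.93 | 61% |
| 0.3 | 0.91 | 2.03 | 65% |
| 0.5 | 0.75 | 2.23 | 72% |
| 0.6 | 0.64 | 2.42 | 78% |

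These figures assume that all 83 per arm have a score at the chosen visit. At 84% completion (0.84 × 83 = 69.7 per arm) the same formula gives 55% unadjusted and 58%, 65% or 71% adjusted. The gain is of similar size.

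**2. Participants kept by a classical complete-case ANOVA.** 0.84 × 166 = 139; 0.60 × 166 = 100; 0.30 × 166 = 50. This is a worst case (see the objection).

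**3. QSU-B, MNWS, mCEQ: which contrast gains precision.** Take 12 post-baseline treatment visits, correlation 0.5 between any two occasions, drop-out unrelated to scores, and 84% completion. SD of the estimated treatment difference, in units of the score SD:

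- Complete-case ANOVA averaged over visits, no baseline: √[2 × (0.5 + 0.5/12) / 69.7] = √(2 × 0.542 / 69.7) = 0.125.
- Mixed model with baseline, Week 12 contrast: 0.144. Week 12 attenders alone, baseline-adjusted, give √(2 × 0.75 / 69.7) = 0.147; the earlier visits add little.
- Mixed model with baseline, averaged over visits: about 0.085. With no drop-out it would be √[2 × (0.25 + 0.5/12) / 83] = 0.084, where 0.25 = 0.5 - 0.5².
- Mixed model averaged over visits without a baseline score: 0.116.

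Moving the question to Week 12 would thus lose precision against even the worst-case ANOVA (0.144 against 0.125). Keeping the whole-study average gains it (0.085 against 0.125). Most of that gain needs a baseline score. Using all available visits alone moves 0.125 only to 0.116.

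**4. Late HADS scores after deterioration.** C3g discontinues participants with gross clinical deterioration and seeks only adverse event and smoking data afterwards, so their later HADS scores may be absent. No document links discontinuation to a HADS value. The size of any bias therefore cannot be derived from the plan.

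**The case against.** - **The ANOVA may not be complete-case.** No implementation is named, and C3f plans to repeat all efficacy analyses as a completers analysis. That repeat would be largely redundant if the main analysis already dropped non-completers. This stands, so 139, 100 and 50 of 166 are worst-case counts and not a forecast.
- **Baseline may already enter.** Time could include Week 0 as a level, and section 4.4 leaves room for adjustment. This stands in part: the right statement is that no baseline term is specified, not that none will be used.
- **Baseline collection is stated for only one of the four scales.** The all-visits heading in C3e covers the psychiatric measures. The section on craving, withdrawal and satisfaction forms gives no schedule for QSU-B, MNWS or mCEQ. This stands, and the recommendation for those scales is conditional on a Week 0 value.
- **Most participants with problems stay in follow-up.** C3d and Human Subjects section 2.2.1 keep those who stop medication in the study for monitoring, and only gross deterioration leads to discontinuation. Such cases still count in the neuropsychiatric adverse event comparison and in the termination reasons by arm. This softens the HADS concern without removing it.

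A reader might infer that the plan hides psychiatric harm, or that it would test HADS at every visit with an inflated false positive rate. Neither is supported. The first would need a discontinuation threshold that no document gives, and the plan nowhere proposes visit-by-visit testing.

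**Conclusion.** The point holds as a minor one confined to secondary analyses. The HADS method as stated is an unadjusted single comparison at an unnamed visit, and a more precise analysis is available from data already planned. The gain is from 61% to between 65% and 78% power for 0.3 SD, if the baseline correlation lies between 0.3 and 0.6. The direction does not depend on the exact correlation; the size does.

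For QSU-B, MNWS and mCEQ the gap is one of specification. The benefit of a mixed model there depends on keeping the whole-study contrast and on a baseline score having been collected.

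Understated worsening in a late HADS comparison is possible but of unknown size. The primary efficacy result and the adverse event non-inferiority analyses are untouched.

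**What to change.** Amend C3f before unblinding.

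1. **HADS.** Use a likelihood-based mixed model for repeated measures on all randomised participants with any post-baseline value. Include treatment, visit, treatment-by-visit, baseline HADS and the two randomisation strata (age group, baseline smoking level). Name one contrast in advance, for example Week 12 to match the primary outcome. Take the planned one-sided test from it and report the difference with a two-sided 95% CI.
2. **QSU-B, MNWS, mCEQ.** Use the same type of model, with the treatment effect averaged over post-baseline visits as the main contrast and Week 12 as supportive. State the collection schedule, and include the baseline score where a Week 0 value exists.
3. **Covariance.** Specify an unstructured covariance with a stated fallback order.
4. **Sensitivity.** Add one delta-adjusted multiple imputation that worsens scores after discontinuation. The mixed model assumes data are missing at random, which is doubtful if deterioration arises between visits and is never scored.

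The cost is SAP wording and modest programming. HADS needs no new data. For the other three scales this holds only if a baseline is already collected; if not, the same model is fitted without that term and the gain is smaller.

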The participant age range (14-21) for the proposed study was chosen for multiple reasons. Broad agreement exists to support this range. The Maternal Child Health Bureau defines adolescence as age 11-21, and the Center for Disease Control and Prevention defines it as ages 10-24. NIH defines individuals up to age 21 as children. Given considerable developmental variability from age 10-24, though, a sample inclusive of this range might be overly heterogeneous. Additionally, while many adolescents initiate smoking between ages 10-13, very few smoke at the rate necessary for study inclusion (only 3% of 8th graders smoke daily, and many of those smoke <5 cigarettes per day) (7). Given the potential identification of individuals 22-24 as adults, we opted to exclude this age range as well. We acknowledge that the previous "adult" varenicline clinical trials included participants as young as age 18, but given the studies' mean age of $43 \pm SD 11$, exceedingly few were age 21 or younger, and there have been no published reports on safety, tolerability, and

efficacy within these younger participants. As such, varenicline remains almost completely unstudied among adolescents, even by the broadest age definition.

We do recognize that the developmental context varies considerably even within the narrowed 8-year range of 14-21. To address this, we plan to stratify randomization by age, ensuring that equivalent proportions of those age 14-17 ("younger adolescents") and those age 18-21 ("older adolescents") are represented in varenicline and placebo treatment groups. Given our prior success in recruiting younger adolescents with high school-based clinics and other strategies, we anticipate recruiting similar proportions of younger versus older adolescents, and will adjust strategies if the proportions become skewed. This stratified approach will convey the added opportunity to compare outcomes (in exploratory fashion) between younger and older adolescents.

C3c. Intake and Randomization

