In keeping with recommendations from an adolescent varenicline pharmacokinetic study (26), participants >55 kg will take varenicline/placebo 0.5 mg once daily for 3 days, titrated to 0.5 mg twice daily for 4 days, titrated to 1 mg twice daily thereafter. Participants ≤55 kg will take varenicline/placebo 0.5 mg once daily for 7 days, titrated to 0.5 mg twice daily thereafter. In our previous experience with varenicline within adolescents, most participants (80%) weighed enough to receive the 2 mg per day dosage.

During weekly visits, study personnel will review medication logs, inspect blister packs, and perform pill counts to monitor medication adherence. Participant compensation at medication visits will be, in part, contingent upon bringing in blister packs and completing medication logs. The study medical clinician

Pro00014398

(physician or physician assistant) will systematically assess medication tolerability and effects, including neuropsychiatric effects (see Section C3e below). Medication supply will be refreshed for ongoing use over the following week. Participants will be encouraged to contact the study medical clinician between visits to address any immediate concerns regarding adverse effects. The study medical clinician will be available "on call" at all times for evaluation and management of adverse events. If a participant experiences intolerable medication-related adverse effects at any point during the study, a dose reduction may be undertaken. If a participant is unable to tolerate the reduced dose, medication will be discontinued, and the participant will be encouraged to remain in the study for monitoring and non-medication study procedures.

Psychosocial Intervention

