The second step towards a sample size analysis is to estimate the effect of varenicline within adolescent smokers. The only existing adolescent varenicline abstinence data come from our recent pilot trial, in which 26.7% of participants achieved cotinine-confirmed 7-day point prevalence abstinence (27). This results in an anticipated effect size (odds ratio) of 5.5. We recognize that this estimate is based on a small sample size ($n=15$ in the pilot trial varenicline group). However, we do not believe the absolute end of treatment 7-day point prevalence abstinence rates from adult varenicline studies (ranging from 50 to 60%) would be appropriate for sample size estimation in this case, as absolute adolescent abstinence rates (see **Table 1**) are consistently lower than those in adult studies (23,24,81). We do, however, believe that varenicline effect sizes may be comparable across adult and adolescent trials. By this measure, our estimates converge. For example, end of treatment abstinence odds ratios in adults were as follows: 3.8 (23), 4.1 (24), and 9.1 (82). Thus, the sample size estimation is based on anticipated abstinence rates of 6.25% (placebo) and 26.7% (varenicline), for an odds ratio of 5.5. With a type 1 error rate of 5% ($\alpha = 0.05$) and power ($1 - \beta$) of 80%, this would require 51 participants per group using a two-sided Pearson's Chi Square test statistic. However, we still wish to aim even more conservatively, recognizing that (a) this effect size may be an overestimate since the varenicline abstinence rate came from a small sample pilot study, and (b) we must account for attrition for the intent-to-treat analysis. In light of the range of odds ratios in prior adult varenicline studies, we have conservatively targeted detection of an odds ratio of 4.0 for power analysis. Original plans were that we will enroll and randomize **83 participants per group**, for a **total sample size of 166**. This will allow us to detect an odds ratio of 4.0 over the anticipated placebo rate of 6.25%, which would correspond to a varenicline abstinence rate of 21.1%. Due to the higher than expected retention losses within our target population of adolescents and following the current ratio of successfully consented to randomized participants, we estimate that 240 participants will need to be enrolled (consented) to meet our sample size needs.

Efficacy: Primary Analysis

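### Pill-count adherence is measured after randomisation, so it should not be a moderator, and the adherent, per-protocol and completer repeats should be reported as non-randomised

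*Combined protocol and SAP*

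**What the plan says.** Section C3f, on secondary smoking-related outcomes, lists pill-count adherence together with nicotine dependence, readiness to quit, self-efficacy, social support and impulsivity, and says that these "will be explored as possible moderators influencing the effect of varenicline on abstinence". The same paragraph says: "All efficacy analyses (primary and secondary) will be repeated among participants with" at least 80% adherence, and again per protocol and in completers. It does not define the last two sets, and it gives no caution on how to interpret any of the three.

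Section C3d (Pharmacological Intervention) has staff "perform pill counts to monitor medication adherence" at weekly visits. The tablet supply is renewed at those visits, with one spare 7-day pack. Participants with intolerable effects may have the dose reduced and then the drug stopped.

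In section C3f the primary efficacy analysis keeps all randomised participants, and "participants will be considered non-abstinent at any missed visit".

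Randomisation is stratified by age, 14-17 versus 18-21 (C3c). Section C3b (Age Range) describes this as an opportunity "to compare outcomes (in exploratory fashion) between younger and older adolescents". Age is not among the moderators in C3f.

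**The concern.** A moderator should be fixed before treatment starts, so that randomisation holds within each of its levels. Every other listed moderator appears under the baseline assessments in C3e. Adherence does not, because it accrues over 12 weeks of treatment.

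The assigned arm can influence adherence in two ways. Side effects may lead some varenicline participants to stop. If the drug works, relapse will differ by arm, and so will the giving-up of tablets and visits that tends to follow relapse. Attendance also affects both sides: supply is renewed and tablets are counted at visits, and a missed visit is scored as smoking. Adherers in the two arms may therefore be different kinds of people.

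At stake is the interpretation. A larger odds ratio among adherers invites the conclusion that the drug works if taken, when it may only reflect who tolerates and continues each tablet. Section C3b already argues that low exposure weakens treatment effects, so that reading would come easily.

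**Working it through.** **1. The plan's own figures.** For "anticipated abstinence rates of 6.25% (placebo) and 26.7% (varenicline), for an odds ratio of 5.5", the plan says "this would require 51 participants per group using a two-sided Pearson's Chi Square test statistic". Use n = [1.96·√(2p̄(1−p̄)) + 0.842·√(p₁(1−p₁) + p₂(1−p₂))]² / (p₁−p₂)².
- 0.0625 versus 0.267 gives 50.5, so 51 per group.
- 0.0625 versus 0.211 (odds ratio 4.0) gives 82.8, so 83 per group.

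Both figures reproduce. The plan gives no figure for the adherence analyses, so the checks below use its 83 per arm.

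**2. Null model A: every abstainer is adherent.** True abstinence is 6.25% in both arms (the plan's placebo rate). Abstinence among adherers is then 0.0625 / adherent share. The documents give no adherence rate by arm. The shares are assumptions within 30-60%, the completion range that C3b reports for earlier adolescent trials.

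| Adherent, varenicline / placebo | Abstinent in subset | Subset OR | Subset rejects | All randomised rejects |
|---|---|---|---|---|
| 60% / 60% | 10.4% / 10.4% | 1.00 | 5% | 4% |
| 45% / 60% | 13.9% / 10.4% | 1.39 | 8% | 4% |
| 30% / 60% | 20.8% / 10.4% | 2.26 | 25% | 4% |

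The true odds ratio is 1.0 in every row. Exchanging the arms in the second row gives 1/1.39 = 0.72, so the error can also favour placebo. If 15% abstain in both arms, the subset rejects 14% (45% / 60%) and 58% (30% / 60%).

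**3. Null model B: motivated and less motivated halves.** The drug again has no effect, and all inputs are assumptions.
- Example 1: abstinence is 12% in the motivated half and 2% in the rest. Adherence is 80% and 40% on placebo, 75% and 15% on varenicline. Among adherers, placebo is (0.40×0.12 + 0.20×0.02)/0.60 = 8.7% and varenicline is (0.375×0.12 + 0.075×0.02)/0.45 = 10.3%, so OR = 1.21. Among non-adherers, placebo is 0.018/0.40 = 4.5% and varenicline is 0.0235/0.55 = 4.3%, so OR = 0.95.
- Example 2: abstinence is 20% and 2%. Adherence is 80% and 50% on placebo, 70% and 10% on varenicline. Adherers: 13.1% versus 17.8%, OR = 1.43. Non-adherers: 7.1% versus 6.5%, OR = 0.90.

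The ratio of odds ratios, adherers to non-adherers, is 1.21/0.95 = 1.28 and 1.43/0.90 = 1.59, where the truth is 1.

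**4. What false effect modification requires.** In simulations (6.25% abstinent), a latent prognostic factor drove both adherence and abstinence.
- Same strength in both arms: the ratio of odds ratios is 0.96-1.00. The subset odds ratio is 1.00 with equal shares, 1.15 at 45% / 60% and 1.37 at 30% / 60%.
- Stronger on varenicline: the subset odds ratio is about 1.5-1.7 and the ratio of odds ratios 2.8-5.8.

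A difference in adherent share alone can therefore bias the subset result. In these runs, appreciable false moderation appeared only when the adherence-prognosis link differed by arm.

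**5. Visibility at this sample size.** Example 1 expects 83×0.0465 = 3.9 abstinent adherers on varenicline and 83×0.052 = 4.3 on placebo. The odds ratio of 1.21 then has an approximate 95% interval of 0.29 to 5.1. The subset test rejects about 6% of the time in example 1 and about 10% in example 2.

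**The case against.** The strongest reply is that nothing confirmatory depends on these analyses. The primary analysis is intent-to-treat, the moderator work is called exploratory, the subset results are repeats, and the plan nowhere draws a causal conclusion from them. That is correct, and it limits the seriousness of the point. It does not make adherence a baseline variable.

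A second reply is that differential adherence is hypothetical. In the adolescent pharmacokinetic study, adverse events occurred in 64% and 73% on varenicline and 13% on placebo. Almost all were mild, however, and nobody discontinued because of them. The 8-week pilot also had no such discontinuations on varenicline (n=15). This stands against assuming a large side-effect difference. Both studies were small or short, and the route through efficacy does not depend on side effects.

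A reader might infer that the bias is built in: whoever stops attending lacks a pill count and is also scored as smoking. The documents do not support that. They give no rule for missing pill counts. C3d encourages those who stop the drug to stay in the study, and C3g seeks smoking data after termination. A non-adherent participant who attends Week 12 can count as abstinent. The link runs through behaviour and is not automatic.

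A reader might also infer that the plan commits itself to an age comparison and then drops it. C3b offers only an exploratory opportunity, so the omission from C3f is a gap between sections and not a broken commitment.

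**Conclusion.** The point holds in a conditional form. Adherence does not belong on the moderator list, and the three repeats are not randomised comparisons. Under no drug effect they mislead if the adherent share or its link to prognosis differs by arm. The direction is not fixed, and identical adherence behaviour in both arms leaves the null comparison unbiased.

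Under the assumptions shown, the false odds ratio among adherers ranges from about 1.2 to 2.3. At 6.25% abstinence, false rejection is mostly 6-11%. The 25% figure needs 30% versus 60% adherent with every abstainer adherent. None of the adherence rates by arm comes from the documents.

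It would be wrong to read this as a threat to the primary result, which uses all randomised participants, or as grounds for deleting the supportive repeats. The change is worth making because it is cheap and prevents an unsupported claim.

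**What to change.** 1. Remove medication adherence from the moderators in C3f, so that the list holds baseline variables only.
2. Add the age stratum (14-17 versus 18-21) as a treatment-by-stratum interaction, labelled exploratory in line with C3b.
3. Keep the adherent, per-protocol and completer repeats. Define each set, including how unreturned packs count, and report the results as non-randomised and supportive, with no conclusion that the drug works if taken.
4. If an effect in adherers is wanted, add a complier-average estimate for Week 12 abstinence only, in all randomised participants with arm as instrument: the difference in abstinence between arms divided by the adherent share on varenicline. State the adherence definition. State also that benefit from partial dosing below the 80% cut-off breaks the exclusion assumption and would inflate the estimate. The Cox and GEE repeats have no equally simple version and need not be replaced.

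The cost is wording for items 1-3 and a little programming for items 2 and 4, on data already collected. The complier interval will be wider. At 6.25% abstinence and 45% adherent on varenicline, its standard error is about √(2×0.0625×0.9375/83)/0.45 = 0.084. The subset difference in the 45% / 60% row above has √(0.139×0.861/37.35 + 0.104×0.896/49.8) = 0.071.
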